**Table 1. Schedule of Assessments**

Weeks	0	1	2	4	6	8	16
	Pre				Mid	Post	Follow-Up
Demographics	X						
Medical/Psych Hx	X						
Mini International Neuropsychiatric Interview (MINI)	X						
World Health Organization Composite International Diagnostic Interview for Bipolar Spectrum Disorders (CIDI)		X					
Duke Activity Status Index (DASI)	X						
The Patient Health Questionnaire (PHQ-9)	X	X	X	X	X	X	X
Altman Self-Rating Mania Scale (ASRM)	X	X	X	X	X	X	X
Sheehan Disability Scale (SDS)		X		X		X	X
Well-Being Index (WHO-5)		X	X	X	X	X	X
Perceived Stress Scale (PSS)		X		X		X	X
Self Efficacy for Exercise (SEE)		X					

International Physical Activity Questionnaire (IPAQ) short form	X	X					
Cardiac Events	X	X	X	X	X	X	X
Seattle Angina Questionnaire – 7 (SAQ-7)*		X				X	X
Adverse Event Questions			X	X	X	X	X

\*The SAQ-7 will only be re-administered to those who respond affirmatively to having angina (coronary artery disease), heart attack, coronary bypass surgery coronary stent or angioplasty procedure or if participant has recurrent chest discomfort with activity that goes away within 10 minutes of rest or with nitroglycerin

#### d. Targeted Enrollment

We expect to recruit a representative sample of the US. We expect that our sample will resemble the general population given the recruitment sites, or MoodNetwork and Health eHeart.

**Table 2. Expected Enrollment by Race, Ethnicity and Gender**

Race	Male (N)	Female (N)	Total (N)
American Indian/Alaska Native	6	7	13 (2.5%)
Asian	12	13	25 (5%)
Black/African American	87	88	175 (35%)
Hawaiian/Pacific Islander	2	3	5 (1%)
White	137	138	275 (55%)
Multiracial	3	4	7 (1.5%)
Ethnicity	Male (N)	Female (N)	Total (N)
Hispanic (Latino/Latina)	50	50	100 (20%)
Non-Hispanic	200	200	400 (80%)
Age	Male (N)	Female (N)	Total (N)
17 years or younger*	----	----	0%
18 to 44 years	125	125	250 (50%)
45 to 64 years	125	125	250 (50%)
65 years or older*	---	---	0%

## V. POTENTIAL BENEFITS

The proposed research study involves an intervention that holds the potential for direct individual benefit such as weight loss, increased healthy lifestyle choices and habits, and decreased medical burden. This research will further our knowledge about medical

burden in depression and the feasibility of psychosocial treatment to reduce this burden. Risks of discomfort associated with the treatment should be offset by the potential physical and mental health benefits. Thus, this study has the potential to not only improve the treatment of depressed patients, but also advance the field by developing a treatment that can be used in future treatment studies of depression.

Subjects will not receive monetary compensation. Subjects will, however, receive the online therapy modules at no cost (if randomized to one of the two therapy-based intervention groups). All participants, regardless of which group they are randomized to, will receive a fitbit device at no cost. For completing the bi-weekly assessments, participants can earn up to \$60 worth of Amazon gift cards. Lastly, participants will have the opportunity to be part of the cutting edge of clinical research.

## **VI. RISKS AND DISCOMFORT**

The risks that this trial poses to participants are reasonable in relation to the anticipated benefits because bipolar disorder is associated with a disproportionately high medical burden as well as chaotic mood swings and a high rate of functional impairment.

The risk of loss of privacy in our study hosted by the Eureka Research Platform and the MoodNetwork will be present for all persons participating. Loss of privacy could occur by compromise of either of the technical systems, or if either are required by law to disclose data to authorities, e.g. to prevent serious harm to the participant or others.

### **Potential Risks to Subjects**

Participants may experience some discomfort or anxiety from discussing personal material and completing self-report questionnaires. If a subject feels uncomfortable responding to a question, he or she will not be required to give a response.

As with any type of physical activity, there is a small risk of physical injury. In order to minimize this risk, we take several steps. First, we ask individuals to participate only if they are healthy enough for mild to moderate physical activity. We ask that if they are not sure, that they check with a physician before continuing with this study. Second, we ask that they do not engage in any exercise practices that cause any physical discomfort or place them at risk of falling. If, for some reason, they do experience an injury while participating in this study, we ask that they contact their primary care physician or visit their local emergency room.

A further risk is a breach of confidentiality. This breach could occur when PII is accidentally made visible to other researchers or to the public. The potential harm from this risk is psychological or social harm from having personal data made public.

### **Protection Against Risks**

We will implement the following procedures to protect participants against risks:

1. Screening procedures will exclude any individuals who are not clinically suitable for the study protocol. For example, individuals will be excluded if they endorse a 3 on item 9 (Suicidal ideation) of the PHQ-9 (i.e., “Thoughts that you would be better off dead or of hurting yourself in some way p nearly every day”) during study intake. Lastly, to protect participants against risks, we will exclude individuals who have any contraindication to exercise or who are at elevated risk for a cardiac event as assessed by the DASI and Cardiac Events questionnaire.
2. Throughout the study, participants will be closely monitored for exacerbation of mental health conditions with the Patient Health Questionnaire (PHQ-9) and Altman Self-Rating Mania Scale (ASRM). Participants who score greater than a total score of a 20 on the PHQ-9 (indicative of “very severe” depression) and/or a total score of a 16 on the ASRM (or indicative of “very severe” mania) will be sent an automated message stating that their response on these assessments suggests that follow-up care with a local provider is warranted. If item 9 (Suicidal ideation) on the PHQ-9 is a 2 or higher (i.e., “Thoughts that you would be better off dead or of hurting yourself in some way on more than half the days”), then an automatic message will also be generated alerting the individual that their response warrants follow-up care with a local provider. Specifically, via embedded web links, we will refer participants to the MoodNetwork resource page and the DBSA “Find a Pro” link, and will encourage people to contact the National Suicide Prevention lifeline number ([name]) and/or online chat service if needed. When automated messages are sent, a flagged email will be sent to the PI, [name]. Based off the patient responses from the assessments, [name] and his fellow study clinicians will determine if it is safe for the participant to continue participating in the study.
3. Patients will complete the brief, bi-weekly survey of potential cardiovascular symptoms (CE) to monitor participants throughout the study. The survey will ask patients whether they have been hospitalized for any of a variety of cardiac conditions. Patients who respond affirmatively to any of the components of the CE (specifically any of the choices 1-7 in question 1) will be automatically prompted to stop engaging in any excessive physical activity (including activity related to study) and to seek medical attention from their primary provider before proceeding. Study staff will be alerted in these situations and may follow-up directly with the participant.
4. Subjects may be withdrawn from the study for any of the following: 1; 1) Elevated risk for a cardiac event as confirmed by Cardiac Events assessment 2) Clinically significant or serious adverse event not consistent with continuation in study, as determined by subject or study clinicians; 3) Subject's decision to withdraw. Any subjects that are withdrawn from the study will be asked to contact their treating physician for any follow up care.

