#### **IV. RESEARCH DESIGN AND METHODS**

##### **Overview**

Given that majority of participants screened will not be eligible, we plan to screen 5000 individuals with the expectation that 10% will be eligible. We propose to recruit 500 eligible

patients from the ongoing MoodNetwork and the Health eHeart Alliance studies who self-report a history of depression and are at elevated risk for cardiovascular events. 40% of participants (2000) will be recruited from MoodNetwork, while 60% (3000) will be recruited from Health-eHeart. Participation will take a total of 16 weeks. During the first 8 weeks, participants will receive online CBT and a fitbit device to track activity, online MBCT and a fitbit device to track activity, or a fitbit device to track activity but no adjunctive therapy. The second 8 weeks are a follow-up period where participants will be asked to continue wearing their fitbit device, but receive no other form of treatment, regardless of which group they were initially randomized to. Participants will use desktop computers, laptops, tablet devices, or phones to participate in this study. These procedures are described in detail below.

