Accessed through a links managed by MoodNetwork.org and Health-eHeart.org, interested participants will sign an online consent form waiver, found in a web portal hosted by the Eureka mHealth Research Platform. Eureka is a multi-tenant system (architecture in which a single instance of a software application serves multiple customers), which is housed on a HIPAA compliant Amazon cloud database. Once the participant has read and electronically signed the waiver of consent form, participants will register for Eureka and then complete a short battery of assessments to determine eligibility. The assessments will consist of 3 standard psychological assessments (The Patient Health Questionnaire [PHQ-9], the Altman Self-Rating Mania Scale [ASRM], and the Mini International Neuropsychiatric Interview [MINI], and 2 cardiac health assessments (The Duke Activity Status Index [DASI], and the International Physical Activity Questionnaire [IPAQ]). They will also be asked to complete a standard demographic form, and their medical and psychiatric histories. If they are not eligible, they will be thanked for their interest and informed that unfortunately, they are not eligible. If found eligible, they will provide their mailing address information so that we can ship them a Fitbit device. Once they receive their Fitbit device, they will return to the study portal to sync their fitbit with our system so that we can collect their step data complete a series of questionnaires, including the World Health Organization Composite International Diagnostic Interview for Bipolar Spectrum Disorders (CIDI), The Patient Health Questionnaire (PHQ-9), The Altman Self-Rating Mania Scale (ASRM), The Sheehan Disability Scale (SDS), The World Health Organization-5 Well-Being Index (WHO-5), the Self Efficacy for Exercise (SEE), the International Physical Activity Questionnaire (IPAQ), the Seattle Angina Questionnaire-7 (SAQ-7) and the Perceived Stress Scale (PSS). Once completed, participants will be randomized to CBT + Fitbit, MBCT + Fitbit, or the Fitbit-only control group. Those who are randomized to one of the two therapy-based treatment groups will be sent to a portal on MoodNetwork.org to access the interventions. Those randomized to the Fitbit-only treatment group will be brought to a page thanking them for their participation, reminding them to wear their fitbit for the next 16 weeks, and informing them that they will be emailed reminders when they need to return to the portal to complete surveys. All participants, regardless of study group, will be asked to return to Eureka in weeks 2, 4, 6, 8, and 16 to complete a battery of assessments and asked questions about adverse events that may have occurred since beginning the study (detailed in Table 1 below).

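### The Cardiac Events survey is described as bi-weekly for the whole study, but none is scheduled between weeks 8 and 16

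*Combined protocol and SAP*

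**What the plan says.** Section VI, Protection Against Risks, lists the procedures that protect participants. Item 3 reads: "Patients will complete the brief, bi-weekly survey of potential cardiovascular symptoms (CE) to monitor participants throughout the study". On content it adds: "The survey will ask patients whether they have been hospitalized for any of a variety of cardiac conditions". Anyone who endorses one of choices 1-7 in question 1 is automatically told to stop excessive activity, including study activity, and to see their primary provider before going on. Study staff are alerted and may follow up.

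Item 4 lists grounds for withdrawal. The first is "Elevated risk for a cardiac event as confirmed by Cardiac Events assessment". The second is "Clinically significant or serious adverse event not consistent with continuation in study, as determined by subject or study clinicians".

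The Overview in section IV fixes the duration: "Participation will take a total of 16 weeks". The last 8 of those weeks are follow-up with the Fitbit still worn. On timing, it says that participants in every arm "will be asked to return to Eureka in weeks 2, 4, 6, 8, and 16 to complete a battery of assessments". Table 1 agrees. Its columns are weeks 0, 1, 2, 4, 6, 8 and 16, and the Cardiac Events row is marked in all seven. The Adverse Event Questions row is marked at weeks 2, 4, 6, 8 and 16.

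**The concern.** The risk section and the visit schedule describe different monitoring in the second half of the study. Item 3 promises a two-weekly cardiac check for the whole of participation, while the schedule provides one check in the last 8 weeks, at the very end.

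Three protections depend on a CE answer: the stop-activity prompt, the staff alert and the first withdrawal criterion. Between weeks 8 and 16 none of them has a scheduled trigger. Activity is expected to continue in that period. Hypotheses 1a and 1b cover daily steps at follow-up, and the therapy arms keep access to material already presented. The participants have, or are at risk of, cardiovascular disease. The trial runs online, so no scheduled visit fills the interval.

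At stake is how soon the study team learns of a cardiac event and issues its prompt. It is also whether the IRB and the DSMB have been given an accurate description of the monitoring.

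**Working it through.** The plan gives no figure to reproduce. The check compares scheduled weeks.

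**Inputs**
- Stated frequency: every two weeks, for the whole study (Protection Against Risks, item 3).
- Length of participation: 16 weeks (Overview).
- Scheduled weeks after randomisation: 2, 4, 6, 8, 16 (Overview, and the CE row of Table 1). Weeks 0 and 1 in the table come before randomisation, which follows the baseline questionnaires.
- Adverse Event Questions: 2, 4, 6, 8, 16 (Table 1).

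The CE row has seven marks for seven columns, and the running text gives the same post-randomisation weeks, so this is not a broken table.

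**Step 1: surveys expected and scheduled**
- Expected: 16 / 2 = 8, at weeks 2, 4, 6, 8, 10, 12, 14, 16.
- Scheduled: 5, at weeks 2, 4, 6, 8, 16.
- Absent: 8 − 5 = 3, at weeks 10, 12, 14.

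**Step 2: longest interval**
- As scheduled: 16 − 8 = 8 weeks.
- If two-weekly: 2 weeks.

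**Step 3: wait from event to next survey, weeks 8-16**

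Assume that events fall evenly over the period, every survey is completed, and only the survey detects events. The mean wait is then half the interval.

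| | As scheduled | Two-weekly |
|---|---|---|
| Longest wait | 8 weeks | 2 weeks |
| Mean wait | 8 / 2 = 4.0 weeks | 2 / 2 = 1.0 week |

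These values express the interval in another form. They do not estimate how many participants are affected, because the documents give no cardiac event rate.

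**Step 4: can the wording be reconciled with the schedule?**
- Item 2 of the same list says that mood is monitored *throughout the study* with the PHQ-9 and ASRM. Table 1 marks both at weeks 0, 1, 2, 4, 6, 8 and 16, exactly as for CE. The phrase can therefore stand for this schedule.
- Section V, Potential Benefits, calls the paid assessments *bi-weekly*, although they follow the same schedule.
- Neither usage makes an 8-week interval two-weekly. If *bi-weekly* meant twice a week, the mismatch would grow: 2 × 16 = 32 surveys against 5.

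The mismatch therefore stands on the text, and loose wording is a plausible cause.

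**The case against.** The strongest reply is that this is one loose adjective. The Overview and Table 1 agree, and study staff would take survey weeks from them rather than from a descriptive sentence in the risk section. Fewer contacts in follow-up are an ordinary choice. No new treatment material is given then, and Table 1 reduces every instrument used in that period to week 16 alone. The exclusion criteria already remove people with heart failure, a survived cardiac arrest, repeated fainting, exertional chest discomfort relieved by rest or nitroglycerin, or a recent cardiovascular hospitalisation.

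Much of this stands. The operative schedule is clear, and the sentence may simply be badly worded. But item 3 is presented as a protection that will be implemented, and its text describes more monitoring than the schedule delivers. One of the two has to change.

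A reader might go further and infer that most cardiac events in follow-up would be found too late, since under even spread only 2/8 = 25% fall within two weeks of the week-16 survey. The documents do not support that. They state a survey frequency and set no time limit for detection. A reader might also infer that participants are unmonitored for 8 weeks. That goes too far as well. Participants keep their own physicians, the second withdrawal ground does not require a CE answer, and staff and the DSMB review adverse events. Since item 3 describes CE as asking about hospitalisation, someone who answers yes has probably already been in care. What remains is that these routes depend on a report made outside the survey schedule, because the Adverse Event Questions share the gap.

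**Conclusion.** The inconsistency is real and minor. After randomisation, 3 of the 8 surveys implied by item 3 are not scheduled. Detection by survey could take up to 8 weeks instead of 2, and the three CE-dependent protections have no scheduled trigger in that interval. The 8-week figure rests on the schedule alone. The mean waits also need the even-spread, full-response and survey-only assumptions, and an event reported by another route would be known sooner.

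The text does not establish that a safeguard has failed or that any participant would be harmed. The likely consequence is later awareness by the study team and a later prompt. The step analysis, the alpha level and the sample size are unaffected.

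**What to change.** Preferred: add the CE form at weeks 10, 12 and 14, both in the Overview's list of assessment weeks and as columns in Table 1. The form has two questions and its prompts are automated. The cost is three short online forms per participant on the existing platform, with slight burden and some extra alert handling for staff.

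Alternative: if the sponsor and the DSMB intend the present schedule, reword item 3 of Protection Against Risks to say that the survey is completed bi-weekly to week 8 and once at week 16. This costs one phrase. It leaves the 8-week interval in place but describes it correctly.

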### **Ensuring Confidentiality**

To minimize risk of loss of privacy, MoodNetwork and the Eureka mHealth Research Platform takes the following steps:

For MoodNetwork, the database and the web portal will be housed on the Partners Research Computing Cloud Infrastructure (DIPR and RFA). The Discovery Information Platform for Research (DIPR) provides a set of virtual services within the Partners secure data center and within the Partners network which consist of virtual servers for web or application hosting, file storage and database management. All systems are secured behind the Partners firewall and follow Partners Healthcare Information Security policies for authenticated, minimum access. All systems are patched, monitored and scanned routinely for vulnerabilities and intrusions by the systems administrator and PHS Information Security. The web server and database server are hosted within the Partners Firewall. The web server makes use of standard 128-bit Secure Socket Layer (SSL) encryption to protect data in transit.

Unique identifiers (UIDs), or strings of letters and numbers containing no PHI, will be used to de-identify the data. MGH will securely store a linking list document, which allows the UIDs from this project to be linked to the UIDs used by the MoodNetwork and Eureka, allowing access to historical medical data stored in these databases. However, no data generated by this project will be inserted into MGH or Partners Healthcare medical records.

The Eureka mHealth Research Platform is hosted on Amazon Web Services (AWS), a cloud-based server system and computing services, similar to those that protect websites used by banks and electronic health record systems. The platform is HIPAA compliant and Eureka follows security guidelines of the U.S. Health Insurance Portability and Accountability Act of 1996 (HIPAA). Specifically, all research data are stored behind a secure firewall, guarded by intrusion detection software, and encrypted at rest and in transit in our Amazon Virtual Private Cloud. Identifying information (name and email address) will be stored in separate (but linked) data tables so that health-related data can be viewed by approved staff as needed without inadvertent association with identifiers when such linkage is not required. In summary, data are coded, the data key is kept separately and securely; electronic data are protected with a password, and all data are stored on a secure network.

We will include the MoodNetwork and Eureka Privacy Policy and Data Security Measures that will be referenced in study onboarding and viewable at any time (please see attached documents to this submission). The statement will inform patients of the risks of loss of privacy, including via technical compromise or legal requirements. We will also make them aware that they are responsible for keeping their login credentials secure.

## **VII. DATA COLLECTION**

All data collection will adhere to HIPAA regulations. Data will be obtained specifically for research purposes and managed using a secure and HIPAA compliant Amazon cloud database managed by the Eureka mHealth Research Platform. All data will be managed

and shared between MGH and USCF per the subcontract agreement. Both teams have separate statistical analysis and engineering teams. Teams can work both together and individually to manage the needs of data gathering, quality assurance, and data management.

These data will be used to evaluate treatment feasibility and acceptability, treatment integrity, efficacy, and possible mechanisms of change.

All data will be managed and shared between the study team and Fitbit per the data-use agreement.

**a. Safety and Monitoring**

The PI ([name]) and the study staff will discuss participant safety in person or via conference call on a regular basis. They will discuss and resolve any safety issues, as such issues arise - for example, the occurrence of adverse events, possible participant withdrawal from the study, or a score of full depression, hypomania/mania or suicidal ideation. [name] will be responsible for preparing a written report that summarizes these discussions and any decisions that are made pertaining to participant disposition. He will also be responsible for determining whether the research should be altered or stopped.

In addition, there will be a Data Safety and Monitoring Board (DSMB) for this study composed of (1) three Massachusetts General Hospital clinical researchers experienced in conducting randomized clinical trials for depression (2) an expert in assessing and treating cardiovascular disease; (3) an expert in biostatistics; and (4) a patient stakeholder with cardiovascular disease. This DSMB will monitor safety issues, including the review of adverse events, the PI's quarterly report of the study's progress, all IRB amendments, and the adequacy and integrity of accumulating data. The purpose of this process is to assess scientific integrity and patient safety issues, and ensure the ethical conduct of the trials. The DSMB will approve the initiation of the study and subject enrollment, and determine if study procedures should be altered or stopped due to evidence of benefit or harm to trial subjects that may be attributable to the study or reasons related to scientific integrity. The PI will submit quarterly reports to the DSMB detailing any study changes, adverse events, subject recruitment and retention, reasons for early termination, and ongoing data reports. The PI will also respond to all DSMB issues and queries.

